7.2. Exclusion Criteria

Subjects are ineligible for enrollment if they meet any of the following exclusion criteria.

- 1. Previous treatment with pembrolizumab, nivolumab, or other anti-PD-1 or anti-PD-L1 agents.
- 2. New York Heart Association Class III or IV (Appendix D) cardiac disease or myocardial infarction within the past 12 months before screening, or preexisting atrial fibrillation.
- 3. History of cerebrovascular accident or transient ischemic attack.
- 4. NSCLC subjects with known brain metastases (exception below)
 - a. Subjects with treated brain metastases who meet all of the following criteria are eligible:
 - i. Stable brain metastases for at least 1 month,
 - ii. No evidence of progression or hemorrhage after treatment,
 - iii. No ongoing requirement for corticosteroids.
- 5. Gastric adenocarcinoma subjects with brain metastases.
- 6. History of active bleeding within the last 3 months requiring transfusion.
- 7. Anti-angiogenic therapy within the last month.
- 8. Subjects with known interstitial fibrosis or interstitial lung disease.
- 9. History of pulmonary embolism or pulmonary embolism found on screening exam.
- 10. Pre-existing carotid artery disease.
- 11. History of DVT with contraindications to pharmacologic anticoagulation.
- 12. History of:
 - a. Pneumonitis that requires oral or IV steroids;
 - b. Or known cases of hepatobiliary diseases (e.g., primary biliary cholangitis, primary sclerosing cholangitis, history of immune-mediated cholangitis);
 - i. Subjects with cholangitis attributed to infectious etiology (e.g., ascending cholangitis, bacterial cholangitis) are eligible if the infection has been fully resolved prior to the screening visit.
 - c. Or known cases of drug-induced hepatobiliary toxicities.

- 13. NSCLC subjects with hypersensitivity to aspirin.
- 14. Gastric adenocarcinoma subjects with contraindications to enoxaparin.
- 15. Autoimmune diseases:
 - a. Active autoimmune disease requiring systemic treatment within the past 3 months
 - b. Documented history of clinically severe autoimmune disease (e.g., colitis, Crohn's disease)*
- 16. Active, uncontrolled bacterial, viral, or fungal infection requiring systemic therapy.
- 17. Known infection with human immunodeficiency virus, active infection with hepatitis B, or hepatitis C.
- 18. Known allergy to hyaluronidase.
- 19. Hypersensitivity to the active substance or ingredients of PEGPH20 and pembrolizumab.
- 20. Known allergy to piroxicam or other NSAIDs.
- 21. Current use of megestrol acetate (within 10 days of Day 1).
- 22. Chronic use of steroids for pain or emesis management.
- 23. Women currently pregnant or breastfeeding.
- 24. History of another primary cancer within the last 3 years that required treatment, with the exception of non-melanoma skin cancer, early-stage prostate cancer, or curatively treated cervical carcinoma in situ.
- 25. Any other disease, metabolic dysfunction, physical examination finding, or clinical laboratory finding that lead to reasonable suspicion of a disease or condition that contraindicates the use of an investigational drug, may affect the interpretation of the results, or may render the subject at high risk for treatment complications.
- 26. Subject inability to comply with study and follow-up procedures, as judged by the Investigator.

7.3. Subject Withdrawal Criteria

7.3.1. Discontinuation of Treatment

The Investigator must guard the subject's welfare and may discontinue study drug treatment at any time when this action appears to be in the subject's best interest. The reason for the subject's withdrawal must be recorded in the subject's electronic case report form (eCRF). Possible reasons for such actions may include, but are not limited to, the following:

- Disease progression (defined in Section 6.1.4).
- AE.
- Any significant protocol violation (e.g., demonstrated lack of treatment compliance, subject starts taking any concomitant anti-cancer therapy).

^{*}Any relevant diseases that are not listed as examples of exclusionary diseases are to be discussed with the Sponsor.

- Withdrawal of consent by an enrolled subject, either for study treatment itself (and subsequent follow-up) or for participation in follow-up.
- Other reasons as determined by the Investigator or Sponsor: a subject may have study treatment discontinued if, in the opinion of the Investigator or Sponsor, it is not in the subject's best interest to continue.
- The subject becomes pregnant (treatment must be discontinued immediately).
- Treatment delay ≥ 21 days.
- Subjects experiencing any TE event that requires full-dose anticoagulation while on study (PEGPH20 will be discontinued; treatment with pembrolizumab may continue as deemed appropriate by the Investigator).
- Gastric adenocarcinoma subjects for whom enoxaparin is discontinued for any reason (PEGPH20 will be discontinued; treatment with pembrolizumab may continue as deemed appropriate by the Investigator).

Subjects who discontinue treatment with PEGPH20 and pembrolizumab should enter long-term follow-up unless they withdraw consent, die, or are lost to follow-up.

7.3.2. Discontinuation from Study

After discontinuing study treatment (PEGPH20 and pembrolizumab treatment), the subject will enter long-term follow-up for assessment of survival and subsequent anti-cancer therapies (Section 8.1.2.4). Long-term follow-up will continue until the subject discontinues from the study. The reason for the subject's discontinuation from the study should be documented in the subject's eCRF. Possible reasons for study discontinuation include the following:

- Death.
- Withdrawal of consent.
- Lost to follow-up.
- Sponsor termination of the study.
- Other.

7.4. Sponsor Study Stopping Rules

Halozyme may terminate this study after informing Investigators at any time. Investigators will be notified by Halozyme (or designee) if the study is placed on hold, completed, or closed. Conditions that may warrant termination of the study include but are not limited to the following:

- The discovery of unexpected, serious, or unacceptable risk to the subjects in the study.
- A decision on the part of the Sponsor to suspend or discontinue testing, evaluation, or development of the product.

8. STUDY PROCEDURES AND ASSESSMENTS

Study procedures for each portion of the study are provided in the tables in Section 3. This section describes evaluations to be done before, during, and after treatment. Section 8.2 provides information on individual study assessments.

When duplicate evaluations are performed before study commencement, the data from the evaluation closest in time to study entry will be recorded. When duplicate evaluations are performed in a given time window, the worst case value will be recorded for safety evaluations, unless otherwise stipulated. Unless otherwise specified, clinical laboratory tests may be performed 1 day earlier than specified in the relevant Study Schedule of Events.

Scheduled clinic attendance should occur within ± 2 days of the specified dates, as long as doses are separated by the appropriate amount of time. Where this is not possible because of extenuating circumstances (e.g., holidays), the reason should be noted and the doses should be separated by at least 45 hours.

8.1. Study Procedures by Visit

8.1.1. Screening

If the following procedures were done as per the standard of care prior to the subject signing the ICF, the results may be used for this study provided they were within the screening window (≤28 days before Day 1): physical examination, vital sign measurements, height, weight and CT/MRI scan.

Note: Plasma samples are required for PEGPH20 PK, hyaluronan, biomarker, and PEGPH20 immunogenicity analysis; serum samples are required for pembrolizumab PK analysis. All subjects will be monitored for study procedure-associated serious adverse events (SAEs) starting from the time of ICF signature as described in Section 10.2.

8.1.1.1. Within 28 Days Prior to Day 1 (Unless Otherwise Indicated)

- Sign and date prescreening ICF for HA testing in Dose Expansion (if applicable, [See Section 8.2.1.1]).
- Sign and date ICF.
- Register subjects into an Interactive Web Response System [IWRS] for screening/prescreening (if conducted in Dose Expansion).
- Confirm availability of and retrieve tumor tissue (refer to Inclusion Criterion #4 for more details). Tumor tissue must be sent to central laboratory to assess HA status for eligibility into the Dose Expansion portion of the study.
- Obtain CT/MRI scan for disease assessment and eligibility review and send to Central Imaging Vendor (CIV) for storage.
- Obtain CT/MRI brain scan to assess potential CNS disease and/or metastases.
- Review inclusion/exclusion criteria.
- Collect medical and prior medication history.

- Optional (at selected sites only): Perform PET/CT scan and DCE-MRI. DCE-MRI scans must be obtained within 14 days prior to Day 1 (first dose of study medication).
- Perform the following assessments: 12-lead ECG, physical examination, vital signs, ECOG Performance Status, height, weight, and urine or serum pregnancy test within 7 days before Day 1 (first dose of study medication) (WOCBP; local laboratory).
- Obtain samples for the following tests and send to the central laboratory: plasma samples for HA level and exploratory biomarkers, thyroid hormones, hematology, blood chemistry (including glucose), urinalysis, coagulation.

8.1.2. Treatment Period

AEs and concomitant medications will be obtained throughout the study and at every visit.

8.1.2.1. Treatment Cycle 1

8.1.2.1.1. Cycle 1 Day 1

Before PEGPH20 and Pembrolizumab Infusion

- Confirm subjects' eligibility based on inclusion and exclusion criteria.
- Perform the following assessments: vital signs, ECOG Performance Status and weight.
- Obtain blood samples for the following tests and send to the central laboratory:
 - Hematology, blood chemistry (including glucose) and coagulation. NOTE:
 Measurements of total bilirubin, ALP, AST, and ALT (as part of blood chemistry) must be obtained prior to dosing (within 48 hours is acceptable). Local laboratories may be used for these measurements. Dosing can only take place if total bilirubin, ALP, AST and ALT values are within the ranges specified in the Inclusion Criteria.
 - Immunogenicity.
 - PEGPH20 PK, plasma HA, and exploratory biomarkers within 2 hours prior to PEGPH20 dosing (as specified in Table 3) (actual collection times to be recorded).
 - Pembrolizumab PK within 2 hours prior to dosing (as specified in Table 3) (actual collection times to be recorded).
- Administer piroxicam (20 mg) at least 1-2 hours prior to the start of the PEGPH20 infusion on the day of dosing (timing will be at the Investigator's discretion based on the piroxicam manufacturer's Prescribing Information and subject's convenience) to minimize the severity of MSEs. Prophylactic use of a proton pump inhibitor is mandated for all subjects while receiving PEGPH20 (e.g. 20 mg omeprazole daily or OTC equivalent).

• Administer enteric-coated 81 mg of aspirin to all NSCLC subjects and 40 mg of enoxaparin (pre-filled syringes of enoxaparin are allowed) to all gastric adenocarcinoma subjects.

PEGPH20 and Pembrolizumab Infusion

- PEGPH20 IV infusion over 10 to 12 minutes (approximately 1 mL/min).
- Pembrolizumab IV infusion over 30 minutes, 4-6 hours after completion of PEGPH20 infusion.

After PEGPH20 and Pembrolizumab Infusion

- Obtain blood samples for the following tests and send to the central laboratory:
 - PEGPH20 PK 15 minutes (±5 minutes), 1 hour (±15 minutes), 2-4 hours and 6-8 hours after PEGPH20 infusion (as specified in Table 3) (actual collection times to be recorded).
 - Plasma HA and exploratory biomarkers 2-4 hours and 6-8 hours after PEGPH20 infusion (as specified in Table 3) (actual collection times to be recorded).
 - Pembrolizumab PK after 2 hours of dosing (as specified in Table 3) (actual collection times to be recorded).

8.1.2.1.2. Cycle 1 Day 2

- Optional at selected sites only: Perform DCE-MRI 24 hours after PEGPH20 infusion.
- Obtain blood samples for the following tests and send to the central laboratory:
 - PEGPH20 PK, Plasma HA, and exploratory biomarkers 24-26 hours after PEGPH20 infusion (as specified in Table 3) (actual collection times to be recorded).
 - PEGPH20 PK 28-32 hours after PEGPH20 infusion (as specified in Table 3) (actual collection times to be recorded).
 - Pembrolizumab PK 24-28 hours after pembrolizumab infusion (as specified in Table 3) (actual collection times to be recorded).
- Administer enteric-coated 81 mg of aspirin to all NSCLC subjects and 40 mg of enoxaparin (pre-filled syringes of enoxaparin are allowed) to all gastric adenocarcinoma subjects.

8.1.2.1.3. Cycle 1 Day 8

Before PEGPH20 Infusion

- Assess vital signs.
- Obtain a hematology blood sample and send to the central laboratory.
- Obtain a blood sample for blood chemistry and send to the central laboratory. NOTE: Measurements of total bilirubin, ALP, AST, and ALT (as part of blood chemistry) must be obtained prior to dosing (within 48 hours is acceptable). Local laboratories

- may be used for these measurements. Dosing can only take place if total bilirubin, ALP, AST and ALT values are within the ranges specified in the Inclusion Criteria.
- Administer piroxicam (20 mg) within at least 1-2 hours prior to the start of the PEGPH20 infusion on the day of dosing (timing will be at the Investigator's discretion based on the piroxicam manufacturer's Prescribing Information and subject's convenience) to minimize the severity of MSEs. The prophylactic use of a proton pump inhibitor is mandated for all subjects while receiving PEGPH20 (e.g. 20 mg omeprazole daily or OTC equivalent).
- Administer enteric-coated 81 mg of aspirin to all NSCLC subjects and 40 mg of enoxaparin (pre-filled syringes of enoxaparin are allowed) to all gastric adenocarcinoma subjects.

PEGPH20 Infusion

• PEGPH20 IV infusion over 10 to 12 minutes (approximately 1 mL/min).

8.1.2.1.4. Cycle 1 Day 15

Before PEGPH20 Infusion

- Assess vital signs.
- Obtain a hematology blood sample and send to the central laboratory.
- Obtain a blood sample for blood chemistry and send to the central laboratory. NOTE: Measurements of total bilirubin, ALP, AST, and ALT (as part of blood chemistry) must be obtained prior to dosing (within 48 hours is acceptable). Local laboratories may be used for these measurements. Dosing can only take place if total bilirubin, ALP, AST and ALT values are within the ranges specified in the Inclusion Criteria.
- Administer piroxicam (20 mg) at least 1-2 hours prior to the start of the PEGPH20 infusion on the day of dosing (timing will be at the Investigator's discretion based on the piroxicam manufacturer's Prescribing Information and subject's convenience) to minimize the severity of MSEs. The prophylactic use of a proton pump inhibitor is mandated for all subjects while receiving PEGPH20 (e.g. 20 mg omeprazole daily or OTC equivalent).
- Administer enteric-coated 81 mg of aspirin to all NSCLC subjects and 40 mg of enoxaparin (pre-filled syringes of enoxaparin are allowed) to all gastric adenocarcinoma subjects.

PEGPH20 Infusion

• PEGPH20 IV infusion over 10 to 12 minutes (approximately 1 mL/min).

8.1.2.1.5. Cycle 1 Day 18

- Optional selected sites only: Perform DCE-MRI and PET/CT scan.
- Perform optional post-dose tumor biopsy at the end of Cycle 1 (on or after Day 18 PEGPH20 dose) but prior to 1st PEGPH20 dose in Cycle 2.

 Administer enteric-coated 81 mg of aspirin to all NSCLC subjects and 40 mg of enoxaparin (pre-filled syringes of enoxaparin are allowed) to all gastric adenocarcinoma subjects.

8.1.2.2. Treatment Cycle 2 and Beyond (Repeats Every 3 weeks)

8.1.2.2.1. Cycle 2 and Beyond, Day 1

Before PEGPH20 and Pembrolizumab Infusion

- Perform the following assessments: vital signs, ECOG Performance Status and weight.
- Obtain blood samples for the following tests and send to the central laboratory:
 - Hematology, blood chemistry (including glucose), coagulation. NOTE for Cycle 2 only: Measurements of total bilirubin, ALP, AST, and ALT (as part of blood chemistry) must be obtained prior to dosing (within 48 hours is acceptable). Local laboratories may be used for these measurements. Dosing can only take place if total bilirubin, ALP, AST and ALT values are within the ranges specified in the Inclusion Criteria. If a subject has any of these values outside the specified ranges on Day 1 of Cycle 2, the Investigator should discuss further dosing plans for the subject with the Sponsor.
 - Immunogenicity.
 - Thyroid hormones (to be collected every third cycle thereafter (i.e., Day 1 of Cycles 2, 5, 8, 11, 14, 17, 20, etc.).
 - Plasma HA and exploratory biomarkers within 2 hours prior to PEGPH20 dosing (as specified in Table 3) (actual collection times to be recorded).
 - Pembrolizumab PK within 2 hours prior to dosing (as specified in Table 3) (actual collection times to be recorded).
- Urine/serum pregnancy test (WOCBP; local laboratory).
- Administer piroxicam (20 mg) at least 1-2 hours prior to the start of the PEGPH20 infusion on the day of dosing (timing will be at the Investigator's discretion based on the piroxicam manufacturer's Prescribing Information and subject's convenience) to minimize the severity of MSEs. The prophylactic use of a proton pump inhibitor is mandated for all subjects while receiving PEGPH20 (e.g. 20 mg omeprazole daily or OTC equivalent).
- Administer enteric-coated 81 mg of aspirin to all NSCLC subjects and 40 mg of enoxaparin (pre-filled syringes of enoxaparin are allowed) to all gastric adenocarcinoma subjects.

PEGPH20 and Pembrolizumab Infusion

- PEGPH20 IV infusion over 10 to 12 minutes (approximately 1 mL/min).
- Pembrolizumab IV infusion over 30 minutes, 4-6 hours after completion of PEGPH20 infusion.

After PEGPH20 and Pembrolizumab Infusion

- Obtain blood samples for the following tests and send to the central laboratory:
 - PEGPH20 PK 15 minutes (±5 minutes), 6-8 hours after PEGPH20 infusion (as specified in Table 3) (actual collection times to be recorded).
 - Pembrolizumab PK 0-2 hours after PEM dose (as specified in Table 3) (actual collection times to be recorded).

8.1.2.2.2. Cycle 2 and Beyond, Day 2

- Obtain blood samples for the following tests and send to the central laboratory:
 - PEGPH20 PK samples 24-26 hours after PEGPH20 infusion (as specified in Table 3) (actual collection times to be recorded).
 - PEGPH20 PK samples 28-32 hours after PEGPH20 infusion (as specified in Table 3) (actual collection times to be recorded).
 - Pembrolizumab PK samples 24-28 hours after PEGPH20 infusion (as specified in Table 3) (actual collection times to be recorded).
- Administer enteric-coated 81 mg of aspirin to all NSCLC subjects and 40 mg of enoxaparin (pre-filled syringes of enoxaparin are allowed) to all gastric adenocarcinoma subjects.

8.1.2.2.3. Cycle 2 and Beyond Day 8

Before PEGPH20 Infusion

- Assess vital signs.
- Obtain blood sample for testing of glucose and send to the central laboratory.
- Obtain a hematology blood sample and send to the central laboratory.
- Administer piroxicam (20 mg) at least 1-2 hours prior to the start of the PEGPH20 infusion on the day of dosing (timing will be at the Investigator's discretion based on the piroxicam manufacturer's Prescribing Information and subject's convenience) to minimize the severity of MSEs. The prophylactic use of a proton pump inhibitor is mandated for all subjects while receiving PEGPH20 (e.g. 20 mg omeprazole daily or OTC equivalent).
- Administer enteric-coated 81 mg of aspirin to all NSCLC subjects and 40 mg of enoxaparin (pre-filled syringes of enoxaparin are allowed) to all gastric adenocarcinoma subjects.

8.1.2.2.4. Cycle 2 and Beyond Day 15

Before PEGPH20 Infusion

- Assess vital signs.
- Obtain a blood sample for testing of glucose and send to the central laboratory.
- Obtain a hematology blood sample and send to the central laboratory.
- Administer piroxicam (20 mg) at least 1-2 hours prior to the start of the PEGPH20 infusion on the day of dosing (timing will be at the Investigator's discretion based on the piroxicam manufacturer's Prescribing Information and subject's convenience) to minimize the severity of MSEs. The prophylactic use of a proton pump inhibitor is mandated for all subjects while receiving PEGPH20 (e.g. 20 mg omeprazole daily or OTC equivalent).
- Administer enteric-coated 81 mg of aspirin to all NSCLC subjects and 40 mg of enoxaparin (pre-filled syringes of enoxaparin are allowed) to all gastric adenocarcinoma subjects.

PEGPH20 Infusion

• PEGPH20 IV infusion over 10 to 12 minutes (approximately 1 mL/min).

After PEGPH20 Infusion

• Optional at selected sites in Cycle 2 only: Perform PET/CT. The CIV will analyze PET/CT scans if they are conducted.

PEGPH20 Infusion

• PEGPH20 IV infusion over 10 to 12 minutes (approximately 1 mL/min).

8.1.2.2.5. Selected Cycles from Cycle 2 Onwards, Day 15

• Obtain CT/MRI scans for tumor assessment (based on RECIST v1.1 and irRC) at the end of Cycles 2, 4, and then at the end of every fourth cycle thereafter (i.e., Week 3 of Cycles 2, 4, 8, 12, 16 and beyond). Scans may be obtained any time on or after Day 15 (of Cycles 2, 4, 8, 12, 16 and every fourth treatment cycle thereafter) to allow enough time for the scan to be reviewed locally prior to the subject's next scheduled dosing visit. The results should be interpreted before dosing in the next cycle begins. For subjects who are withdrawn from the study due to clinical disease progression, a CT/MRI scan should be requested as soon as possible after clinical progression is determined.

Note: A confirmatory scan should be performed no sooner than 28 days if the initial scan showed a response (PR or CR) based on RECIST v1.1 and irRC. A confirmatory scan should also be performed to confirm disease progression based on irRC no sooner than 28 days after the initial scan that showed progression.

• For the duration of the study, post-baseline, CT/MRI of the brain will be performed if clinically indicated, and within a target of 1 week after a subject achieves a CR. For

NSCLC subjects with a history of treated brain metastases, brain scans will be performed at tumor assessment time points.

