PEGPH20 Pharmacokinetics Immunogenicity Plasma Hyaluronan Exploratory Biomarkers Pembrolizumab Pharmacokinetics		Unscheduled	X	X	X	X	X	X

Abbreviations: D = day; HA = hyaluronan; PEM = pembrolizumab.

Notes: Pembrolizumab PK samples will be collected and analyzed when a validated assay is available. If a subject discontinues PEGPH20 therapy, PEGPH20 PK samples will not be collected from that subject. However, if that subject continues on pembrolizumab therapy at the discretion of the Investigator, pembrolizumab PK samples must be collected.

Plasma samples are required for PEGPH20 PK, plasma hyaluronan, biomarker, and PEGPH20 immunogenicity analysis; serum samples are required for pembrolizumab PK analysis.

^a PEGPH20 Immunogenicity.

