4.5.9. Clinical Pharmacokinetics

Subjects enrolled in the Phase 1 studies received PEGPH20 at doses ranging from 0.5 to 50 μ g/kg with or without dexamethasone. Blood samples were collected at scheduled time points, and plasma was analyzed for PEGPH20 concentrations. PK analysis suggests that a linear PK model adequately described the available PEGPH20 plasma concentration versus time profiles. The maximum plasma concentrations were estimated to be between 0.4 and 1.0 hours after dosing. Subjects dosed with 50 μ g/kg PEGPH20 in Study HALO-109-101 demonstrated a plasma half-life of 2.5 to 4.8 hours for the initial phase and 26 to 49 hours (1 to 2 days) for the terminal phase. Estimates for initial distribution volume were consistent with expectations for therapeutic macromolecules. The prolonged plasma half-life of PEGPH20 makes sustained depletion of tumor-associated HA feasible. Clinical experience to date (largely involving combination therapy with GEM) indicates that the linear PK characteristics of PEGPH20 given alone are maintained in combination therapy. Details of the PK characteristics of PEGPH20 are provided in the PEGPH20 Investigator's Brochure.

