5.2. Study Endpoints

5.2.1. Dose Escalation

Primary Endpoint

• Dose-limiting toxicity, MTD, and RP2D.

Secondary Endpoints

- PK parameters of PEGPH20: maximum observed concentration (C_{max}), minimum observed concentration (C_{min}), terminal elimination half-life ($T_{1/2}$), area-under the-concentration-time curve (AUC), volume of distribution (V_D) and clearance (CL).
- ORR, DOR, DCR and PFS based on RECIST v1.1.
- OS.

Exploratory Endpoint

• PK parameters of pembrolizumab: C_{max}, C_{min}, T_{1/2}, AUC, V_D and CL.

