5.2.2. Dose Expansion

Primary Endpoint

• ORR based on RECIST v1.1.

Secondary Endpoints

- DOR, DCR and PFS based on RECIST v1.1, and OS.
- ORR, DOR, DCR and PFS based on irRC.
- PK parameters of PEGPH20: C_{max}, C_{min}, T_{1/2}, AUC, V_D and CL.
- Incidence of AEs.
- Changes in clinical safety laboratory values.

• Changes in cardiovascular parameters (electrocardiogram [ECG]) and vital signs.

Exploratory Endpoints

- ORR, DOR, DCR, and PFS based on RECIST v1.1 criteria and irRC by PD-L1 expression levels.
- Changes from pre-treatment in plasma HA and tumor HA (when available).
- Correlation between plasma HA levels pre-dose, post-dose and any pharmacodynamic response.
- Changes in tumor blood flow as measured by DCE-MRI.
- Changes in tumor metabolism as measured by PET/CT.
- Correlation of biomarkers in plasma and tumor biopsy to study endpoints.
- PK parameters of pembrolizumab: C_{max} , C_{min} , $T_{1/2}$, AUC, V_D and CL.

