8.3. Study Drug Administration

Each treatment cycle is 21 days (3 weeks).

In Dose Escalation, PEGPH20 will be administered on Day 1, Day 8 and Day 15 of each 21-day cycle (i.e. 3 doses/cycle) and pembrolizumab (2 mg/kg every 21 days) on Day 1 of each cycle (i.e. 1 dose/cycle), 4-6 hours after the completion of PEGPH20 administration.

In Dose Expansion, PEGPH20 will be administered on Day 1, Day 8 and Day 15 of each 21-day cycle (i.e. 3 doses/cycle) and pembrolizumab (200 mg every 21 days) on Day 1 of each cycle (i.e. 1 dose/cycle), 4-6 hours after the completion of PEGPH20 administration.

Treatment in both portions of the study will continue until disease progression or unacceptable toxicity, death, or withdrawal of consent from the study.

If a dose of PEGPH20 is missed on Day 1 of cycle 2 or beyond, the cycle will continue as scheduled. If it is known that pembrolizumab will be missed or held on Day 1, PEGPH20 should also be held and the cycle will not start until the first dose of pembrolizumab is administered. This will require planning such that the dose of PEGPH20 can be given before the pembrolizumab dose is set to resume.

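### PEGPH20 Cmin cannot be observed as a trough and per-subject noncompartmental half-life is unreliable, because PK sampling ends at 28-32 h of a 168 h interval; the existing Cycle 2+ pre-dose plasma draw could supply the missing point

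*Protocol*

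**What the plan says.** **Endpoints.** Protocol 5.2.2 lists "PK parameters of PEGPH20: C_{max}, C_{min}, T_{1/2}, AUC, V_D and CL" as secondary for Dose Expansion. Section 5.2.1 lists the same parameters for Dose Escalation and expands Cmin as the minimum observed concentration. SAP 4.3.1 and 4.3.2 repeat both lists.

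**Dosing.** Section 8.3: "PEGPH20 will be administered on Day 1, Day 8 and Day 15 of each 21-day cycle". The gap from Day 15 to the next Day 1 is thus also 7 days.

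**Sampling (Table 3; 8.1.2.1 and 8.1.2.2).**
- Cycle 1 Day 1, pre-dose: PEGPH20 PK is drawn, before any drug has been given.
- Cycles 2+, Day 1, pre-dose (draw 1HAI): "Plasma HA and exploratory biomarkers within 2 hours prior to PEGPH20 dosing", plus immunogenicity. PEGPH20 PK is not listed.
- Post-dose PEGPH20 PK, Cycle 1: 15 min, 1 h, 2-4 h, 6-8 h, 24-26 h and 28-32 h.
- Post-dose PEGPH20 PK, Cycles 2+: 15 min, 6-8 h, 24-26 h and, last, "PEGPH20 PK samples 28-32 hours after PEGPH20 infusion".
- Day 8 and Day 15: no PK draw. Only an unscheduled row in Table 3 would allow a later sample.

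**Known kinetics.** Section 4.5.9 gives "26 to 49 hours (1 to 2 days) for the terminal phase" and 2.5-4.8 h for the initial phase. Section 4.4 attributes these figures to 2 subjects dosed at 50 µg/kg.

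**Analysis.** Section 11.1.7.1 plans noncompartmental and compartmental modelling. AUC, Cmax and half-life are to be summarised from the noncompartmental analysis. Population estimates of half-life, VD and CL follow only where the data allow. Cmin is not mentioned there. SAP 4.3 and 4.4.4 defer all PK analysis to a separate plan, which is not among the documents.

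**Matrix.** Table 3 notes: "Plasma samples are required for PEGPH20 PK, plasma hyaluronan, biomarker, and PEGPH20 immunogenicity analysis".

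**The concern.** A trough and a terminal half-life both need information from late in the dosing interval. The schedule collects none after 32 h of a 168 h interval, yet pre-dose plasma is already taken each cycle at the right moment and assayed for other things. Pembrolizumab PK, which is only exploratory, does get a pre-dose sample every cycle; PEGPH20 PK, which is secondary, does not.

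At stake is whether the reported Cmin has any meaning and whether the individual half-lives can be used. AUC to infinity, CL and VD are also affected, because each relies on the terminal slope. Section 8.2.16 says the plasma samples are meant to show whether pembrolizumab alters PEGPH20 PK; a change in slow elimination would show mainly in the part of the curve that is barely sampled.

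**Working it through.** The 26-49 h half-life cannot be re-derived, because no concentrations are given. Only the conversion to days can be checked: 26/24 = 1.08 and 49/24 = 2.04, which agrees with the stated 1 to 2 days.

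**Inputs from the documents:** terminal half-life t½ = 26-49 h; initial half-life 2.5-4.8 h; dosing interval 168 h; last two samples at 24-26 h and 28-32 h, so 2 to 8 h apart. **Assumptions, not in the documents:** assay CV 10% at 28-32 h and 20% at 168 h; trough above the assay limit.

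**1. Coverage of the terminal phase (time / t½).**
- 32 h: 32/49 = 0.65 to 32/26 = 1.23 half-lives.
- 168 h: 168/49 = 3.4 to 168/26 = 6.5 half-lives.

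**2. The 32 h value against the 168 h trough (ratio 2^((168 − 32)/t½)).**
- t½ = 49 h: 2^(136/49) = 6.8.
- t½ = 26 h: 2^(136/26) = 37.6.
- A sample at 28 h would give slightly larger ratios: 2^(140/49) = 7.2 and 2^(140/26) = 41.8.

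**3. How many samples are terminal.** Five initial half-lives take up to 5 × 4.8 = 24 h, so only the last two samples lie clearly beyond the initial phase. From 25 h to 30 h the concentration falls by 1 − 2^(−5/26) = 12.5% or 1 − 2^(−5/49) = 6.8%, which is close to the size of the assumed assay error.

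**4. Precision of the two-point slope for one profile (CV = √2 × 0.10 / (ln 2 × Δt / t½)).**
- Best case, Δt = 8 h, t½ = 26 h: 0.1414/0.2133 = 66%.
- Mid-window (25 and 30 h), Δt = 5 h: 106% (26 h) to 200% (49 h). The chance of a flat or rising slope is 17-31%.
- Worst case, Δt = 2 h, t½ = 49 h: 0.1414/0.0283 = 500%.

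**5. Using the 6-8 h sample as a third point.** This brings in the initial phase. With an assumed terminal intercept fraction of 0.1-0.5, the apparent half-life is about 8-33 h when the truth is 26-49 h. Under the same assumption, 18-62% of AUC lies beyond 30 h and must be extrapolated.

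**6. Pooled modelling.** A naive pooled two-compartment fit to one Cycle 1 profile from each of 51 subjects (assumed log residual SD 0.15, same intercept range) gives a relative standard error of the terminal half-life of about 17-102%. This leaves out between-subject variability, which would worsen it, and repeat cycles, which would improve it.

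**7. With the 168 h sample added.** The error of the log difference is √(0.10² + 0.20²) = 0.224, and from 28 h Δt = 140 h.
- t½ = 26 h: 0.224/(ln 2 × 140/26) = 0.224/3.73 = 6%.
- t½ = 49 h: 0.224/(ln 2 × 140/49) = 0.224/1.98 = 11%.

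As a cross-check, the individual two-compartment fit (SD 0.15 at every point) improves from a relative standard error of 123-732% to 5-17%. The trough follows the Day 15 dose rather than the sampled Day 1 dose. Weekly accumulation of the terminal phase is 1/(1 − 2^(−168/t½)) = 1.01-1.10, so under linear kinetics with no missed dose this matters little.

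**The case against.** A reader might infer that neither Cmin nor half-life can be estimated at all and that any half-life from this trial is noise. The documents do not support that. Section 11.1.7.1 also plans compartmental modelling and, where the data suffice, population estimates. Cycles 2+ repeat four post-dose samples each cycle with actual times recorded. The 66-500% describes one subject, one cycle and two points; step 6 shows that a study-level mean of poor to moderate precision is attainable, and a model could also predict a trough.

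Other points stand in part:
- Section 5.2.1 words Cmin as the lowest concentration observed, not as a steady-state trough, and 11.1.7.1 gives no Cmin summary. The 7- to 38-fold ratio therefore applies only if the 32 h value is read as the end-of-interval level. The literal definition does not help, however: it returns either the value before the first dose or the 28-32 h value, and neither describes the end of the interval.
- The separate PK plan might handle AUC and Cmin sensibly. It cannot create samples that were not scheduled.
- The half-life comes from a dose 12.5 to 50 times those used here (50/4.0 to 50/1.0). A 168 h level of about 2.5-14% of the 30 h level may fall below an assay limit that the documents do not state.
- Visit windows of ±2 days and held doses move the trough away from 168 h. Recorded sampling and infusion times deal with the timing, but not with between-occasion variability.
- Escalation and MTD follow DLTs, and the RP2D follows overall safety. No decision rule uses Cmin or half-life.

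**Conclusion.** The point holds in a limited form. As scheduled, PEGPH20 Cmin cannot be observed as a trough, and the per-subject noncompartmental half-life planned in 11.1.7.1 is unreliable. That weakness carries into extrapolated AUC, CL and VD. A study-level half-life from compartmental or population modelling remains possible.

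The size is a 32 h value about 7 to 38 times the expected 168 h level, and a two-point slope CV of about 66-500%. Both rest on the quoted 26-49 h half-life from 2 subjects; the second also rests on an assumed 10% assay CV. The improvement to about 6-11% further assumes a 20% CV at 168 h and a trough above the assay limit.

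Severity is low: these are descriptive secondary endpoints, and no primary endpoint or dose-escalation rule depends on them. It is a cheap improvement, not a threat to the trial's conclusions.

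**What to change.** In Table 3 and in 8.1.2.2.1, add PEGPH20 PK to the existing 1HAI pre-dose plasma draw on Day 1 of Cycles 2+. In the separate PK plan:
- define this sample as the observed trough and use it as a late terminal-phase point;
- use the actual time since the last PEGPH20 dose, not the nominal 168 h;
- report values below the assay limit as such;
- state how Cmin is summarised, since 11.1.7.1 does not.

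The cost is extra assay runs on plasma that is already collected, with no added visit or venepuncture. Before adopting it, confirm in the Laboratory Manual that the 1HAI tube, volume and handling suit the PK assay, and check the assay limit against the expected trough. If many troughs are below the limit, the gain in half-life precision will be partly or wholly lost, although the trough would then at least be known to lie below that limit.
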